### d. Early stopping rules.

After 5 and 10 participants complete testing we will evaluate the data to look for themes and determine if further testing is likely to yield additional information. If a large percentage of patients are unable to complete the study due to complaints with device comfort or due to previously defined adverse outcomes we will halt the study.

## 8. Risks

### a. Medical risks, listing all procedures, their major and minor risks and expected frequency.

Application and wearing of any of the experimental or existing nasal dilators could conceivably lead to:

1. Discomfort, including moderate temporary pain, or irritation, including tickling that may cause sneezing. Discomfort associated with wearing the devices is expected to be uncommon, minor, and self-limited. Participants have the option to refuse or remove any or all of the nasal dilator system at any point.

2. Epistaxis (nose bleeding), is unlikely given that patient with abnormal nasal mucosa are not included in the study. Participants will be trained and assisted by study personnel to atraumatically apply and remove the nasal dilator devices. Should a participant experience epistaxis they will be managed according to the standard of care, which would involve application of manual pressure to the cartilaginous portion of the nose for 20 minutes. Should bleeding be severe or persistent they will be seen by an Otolaryngologist for further management and treatment.

3. Migration of nasal dilator device is highly unlikely given the pre-clinical testing of nasal dilators in a nose model under extreme conditions of high airflow that could be associated with sneezing and peak inspiratory breathing. Additionally, the normal nasal anatomy, namely the inferior nasal turbinates, limit the open space in the nose and should prevent migration of nasal dilators. Individuals with markedly abnormal inferior turbinates are excluded from this study.

4. Nasal dilators may be ineffective at improving nasal airflow during the study. These subjects will not be excluded but may leave the study.

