Participants are free to wear the assigned nasal dilator at their leisure beyond one hour, but must log the hours and activities performed while wearing the device (for example, “10am-11am exercising”). Patients are not required to wear a device in public at work or during exercise unless they feel comfortable doing so. All devices should be worn overnight. When the schnozzle is utilized at night, a modified version will be used where each portion inserted into the nares will be connected by an external bridge. This is to prevent posterior displacement of the device during sleep. Each morning, the participant will complete a survey summarizing their experience using the assigned device (Appendix B). If there is any discomfort, irritation, skin breakdown, or epistaxis the participant should stop wearing the device and contact the research team immediately.

Over the course of the first six days since the initial clinic visit, the participant will trial and log their use of each of the six nasal dilators. After at least six days (one day per device) participants will return to the office for an exit interview with the study team in regards to their subjective experience with each device. At the end of each trial day they will be asked to fill out a concluding survey (see appendix C). At their exit interview they will be asked to submit both appendix B and C for each device they trialed.

Before returning to the clinic for the conclusion of the study, participants may have several days without an assigned device. Participants are free to stop wearing all devices or use any device as they please as long as it is consistent with proper care and use of the device(s).

*b. Study duration and number of study visits required of research participants.*

This study requires two office visits – one to begin the study with baseline PNIF measurements, device fitting, PNIF with each device in place, and a perception survey. This will be followed up with a wrap up visit end the study with a concluding survey. Each patient will participate in the study for at least six days to trial each device, and the entire duration depends on an individual patients’ ability to return to the clinic, no more than two weeks.

Participants will be free to stop participating at any point during the study. Participants will have the option to be included in a list of individuals who would be interested and willing in participating in additional study sessions.

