*c. Blinding, including justification for blinding or not blinding the trial, if applicable.*

Patients will be blinded to the names of the devices tested to limit bias when they complete the surveys. They will also be blinded as to which device was designed by members of the research team.

*d. Justification of why participants will not receive routine care or will have current therapy stopped.*

The standard of care is to do nothing, use existing nasal dilator devices, or surgery. This one session comparison study of nasal dilators does not prevent patients from proceeding with the standard of care after the study session, and will familiarize them more thoroughly with available treatment options.

*e. Justification for inclusion of a placebo or non-treatment group.*

Participants will serially wear the prototype Schnozzle device and marketed nasal dilators, all of which are treatments. We will get a baseline NOSE and PNIF score from participants without any assistive devices in place, which serves as the placebo/ non-treatment arm of the study. Following the study session participants can continue to use currently marketed nasal dilators or proceed with planning surgery.

*f. Definition of treatment failure or participant removal criteria.*

Participants will be removed from the study if they experience substantial discomfort with the study devices, or if they experience any adverse events, such as epistaxis, or skin breakdown or if they would like to discontinue testing for any reason.

*g. Description of what happens to participants receiving therapy when study ends or if a participant's participation in the study ends prematurely.*

At the end of the study session participants will be able to continue using any of the marketed nasal dilator products currently on the market, and this study will not influence their ability to proceed with scheduling surgery if indicated and desired. They will not be able to continue using the Schnozzle nasal dilators at this time as it is still in early stage development and not widely produced or available.

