## 7. Study Statistics

### a. Primary outcome variable.

Peak Nasal Inspiratory Flow (PNIF) and Nasal Obstruction Symptom Examination (NOSE) score for each individual before the trial and while using each tested nasal dilator.

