### c. Statistical plan including sample size justification and interim data analysis.

The purpose of this pilot study is to understand patient needs and preferences regarding nasal dilators, and to use this data to refine the design before potentially marketing the product. In this pilot study we plan to test 70 individuals with nasal valve collapse. Previous studies have demonstrated an ability to detect a statistically significant difference in PNIF with a power of 80% and an alpha of 0.05 with a sample size of 30 patients with nasal valve collapse. We aim to recruit 70 individuals, 35 patients with nasal valve collapse, 35 patients without nasal valve collapse with expected attrition of 5 patients in each cohort.[12] If we proceed to pursue statistical evaluation of the data we will use ANOVA with a  $p < 0.05$  predetermined as significant.

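### Lack of effect is a named route out of the study, so an ANOVA restricted to people with all six devices could overstate the NOSE benefit of dilators over unaided breathing

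*Combined protocol and SAP*

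**What the plan says.** - **Leaving for lack of effect.** Section 8a, item 4, lists this possibility among the risks: "Nasal dilators may be ineffective at improving nasal airflow during the study". It continues: "These subjects will not be excluded but may leave the study".
- **Other exits.** Section 4f provides that "Participants will be removed from the study if they experience substantial discomfort with the study devices", and also for adverse events or at the person's own wish. Section 4b adds: "Participants will be free to stop participating at any point during the study".
- **Primary outcome.** Section 7a names PNIF and the NOSE "score for each individual before the trial and while using each tested nasal dilator". Under section 4e the untreated comparator is each person's own baseline.
- **Timing.** Under section 4a, PNIF is measured with all six devices at the first visit. The devices are then used at home, one per day for six days. On the home forms: "At their exit interview they will be asked to submit both appendix B and C for each device they trialed".
- **Analysis.** Section 7c names ANOVA, and only if statistical evaluation is pursued. It allows for "expected attrition of 5 patients in each cohort". It does not state the type of ANOVA, the analysis set, a rule for missing data or a sensitivity analysis.

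**The concern.** Part of the primary objective is effectiveness against unaided breathing. When people leave because the dilators did not help, missingness depends on the effect being estimated. Someone who leaves on home day 2 has no readings for the later devices. Nothing says that forms already filled in are collected from a person who never reaches the exit interview, so all of that person's home data may be lost. A standard repeated-measures ANOVA then drops the person, and those left are people who did better than average.

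The error favours the devices. Section 9 expects the trial to supply clinical evidence for redesign towards a marketable product, so an inflated gain over unaided breathing would feed that decision. This differs from removal for discomfort under section 4f, because here the reason for leaving is the efficacy outcome itself.

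**Working it through.** **1. The plan's own figure.** Recruits per cohort = 30 / (1 − 5/35) = 30 / 0.857 = 35, and 2 × 35 = 70. This reproduces. (Section 7c also speaks of 70 people with nasal valve collapse; that needs reconciling but does not affect this point.) The 80% power at n = 30 cannot be checked, as no effect size or SD is given. Solved backwards, a paired comparison with n = 30 and two-sided alpha 0.05 detects 0.51 SD (normal) or 0.53 SD (t).

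**2. Upper bound.** Let p = 5/35 = 1/7 leave. If they are exactly the people with the least improvement, the completers' mean rises by φ(z_p)/(1 − p) = 0.26 SD, where z_p is the normal quantile at p. That is about half of the detectable effect in step 1. For an assumed SD of improvement of 10, 15, 20 or 25 NOSE points it is 2.6, 3.9, 5.3 or 6.6 points.

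**3. Simulation of the six home days.** From the documents: 35 per cohort, six devices in random order, 5 of 35 leaving. Assumed, because no NOSE figure is given: true mean gain 15 points; between-person SD 8 to 15; day-to-day SD 10 to 15; exit only after a device-day with a gain under 5, at a rate tuned to 5 of 35. The SD of a person's six-day mean gain is √(person² + daily²/6). The bound is 0.263 times that SD, and the standard error at n = 30 is that SD divided by √30.

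| Person SD / daily SD | Completers' mean | Excess over 15 | Excess % | Bound | SE, n = 30 |
|---|---|---|---|---|---|
| 8 / 10 | 16.4 | 1.4 | 9% | 2.4 | 1.6 |
| 12 / 10 | 17.1 | 2.1 | 14% | 3.3 | 2.3 |
| 15 / 10 | 17.6 | 2.6 | 17% | 4.1 | 2.8 |
| 15 / 15 | 17.1 | 2.1 | 14% | 4.3 | 3.0 |

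Every excess lies below its bound. If half of the attrition is for inefficacy, the excess is 4% to 8%, or 0.6 to 1.2 points. With a true gain of zero, and all attrition for inefficacy, completers show about 0.6 to 1.4 points.

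**4. A different leaving rule.** Let the chance of leaving rise gradually as the mean gain so far falls, with the same 14.3% attrition and within-person correlation 0.3 to 0.7. At an SD of 20 the completers' excess is 0.6 to 4.0 points; over SD 15 to 25 it is 0.4 to 5.1. It is essentially zero when leaving is unrelated to benefit.

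**5. All recorded device-days.** In the settings of step 3, a random-intercept model fitted to the recorded gains returns 15.0 throughout. Fitted with unaided breathing as one of the conditions, it returns 14.9 to 15.4. If leaving depends on true benefit that the readings do not capture, the model of gains keeps an excess of about 0.4 to 0.8 points, against 1.6 to 3.2 for completers. Setting missing days to baseline gives 14.3 to 15.0.

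**The case against.** Several points on the other side stand.

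- **Completers-only analysis is inferred.** Section 7c says only ANOVA. A reader might infer a planned restriction to people with all six devices, but no such restriction is written. It is the usual consequence of a repeated-measures ANOVA, and the step from 35 to 30 is consistent with it.
- **Home collection of NOSE is inferred.** The documents place NOSE explicitly only at baseline. Section 7a requires it "for each individual before the trial and while using each tested nasal dilator" without giving a time, and the content of Appendices B and C cannot be seen.
- **Item 4 is a risk disclosure.** It keeps non-responders in the study and otherwise echoes the general right to stop. A reader might infer that they are encouraged to go, or that the trial enriches for responders; the text supports neither. It also speaks of airflow, and PNIF, the airflow measure, is mostly complete after visit 1.
- **No cause is given for the 5 of 35.** Discomfort, adverse events and difficulty in returning to clinic are alternatives, so 9% to 17% is the case in which inefficacy explains every loss. Even then the excess is only 0.7 to 0.9 of a standard error at n = 30 (2.1/3.0 to 2.6/2.8).
- **A 15-point gain is doubtful for the cohort without valve collapse.** The zero-effect result may be nearer for them.
- **Comparisons between devices are less affected**, because order is randomized within person, and this is a pilot.

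These points make the claim conditional and limit its size. They do not supply an analysis set, a rule for missing data or a way to recover leavers' forms.

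**Conclusion.** The concern holds as a conditional statement. If on-device NOSE is gathered over the home days, and the analysis drops people without all six devices, the device-versus-unaided NOSE benefit could be overstated. Under the assumed values the excess is about 9% to 17% if all 5 of 35 leave for inefficacy and 4% to 8% if half do; a spurious 0.6 to 1.4 points appears when there is no true effect. The direction follows from the link between leaving and poor benefit. The size rests on assumptions, because the documents contain no NOSE mean or SD.

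Two wider conclusions are not supported: that the PNIF results or the ranking of devices are seriously biased, and that a mixed model removes the problem entirely. It does so only as far as leaving depends on recorded readings. The change should be made, preferably before data collection, since forms and reasons not collected when a person leaves may be unrecoverable.

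**What to change.** **Section 7c.** Define the analysis set as everyone fitted at visit 1. Analyse all recorded device-days with a linear mixed model (participant random; condition fixed, including unaided) instead of an ANOVA on people with all six devices. Add one sensitivity analysis that sets missing device-day NOSE to the person's own unaided baseline for those who left because dilators did not help. State when on-device NOSE is collected.

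**Section 8a, item 4.** Ask a person who leaves to hand in the log and forms completed so far, and record the reason. Report these exits by cohort and last device worn. The right to leave is unchanged.

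**Cost.** A few sentences in two sections and one reason-for-leaving field. The estimated benefit over unaided breathing may look less favourable. Leavers may decline to return forms. Some excess may remain where leaving depends on experience that was not recorded; the sensitivity analysis shows how far the result depends on this.

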### b. Steps taken to minimize the risks.

Included in each risk above.

*c. Plan for reporting unanticipated problems or study deviations.*

Any unanticipated problems, adverse events, or study deviations will be immediately discussed with the principal investigator (PI) and reported to the IRB if deemed appropriate by the PI. This will be done using RF3 and RF4 as needed.

*d. Legal risks such as the risks that would be associated with breach of confidentiality.*

All collected data will be stored on an encrypted drive password protected as per protocol. Patient data will be de-identified and not have a name or date of birth associated with it.

*e. Financial risks to the participants.*

Participants' only financial risk is the opportunity cost associated with their time spent in office at the beginning and end of the trial.

## **9. Benefits**

*a. Description of the probable benefits for the participant and for society.*

By participating in this study, individuals with nasal valve collapse will have an opportunity to trial several existing nasal dilators. In typical clinical practice patients are given recommendations for several types of nasal dilators but are not fitted and trained in appropriate use. Participants may notice a marked improvement in their ability to breathe while wearing the devices and an enhancement in quality of life.

Schnozzle has the potential to improve of the quality of life for the millions of nasal obstruction sufferers who currently forgo treatment. Faced with the choice between inaction and the appointments, extensive recovery period, and uncertain outcome inherent with surgery, the majority of individuals—especially those with minor to moderate obstruction—elect to live with their symptoms, which present a constant bother, source of embarrassment, and long-term health risk.

While existing nasal dilators are effective in temporarily relieving their symptoms, sufferers agree that existing products are not an option for use in their daily lives. However, these same individuals insist that a comfortable and discreet device would present a preferred solution to surgery to aid their breathing during the day. This trial will provide the clinical evidence necessary to evaluate and inform redesigns of existing prototypes to aid in the development of a finalized product ready for the market.

## **10. Payment and Remuneration**

*a. Detail compensation for participants including possible total compensation, proposed bonus, and any proposed reductions or penalties for not completing the protocol.*

Participants will not be paid, but they will be given the option to keep any of the marketed nasal dilators they trialed (Breathe Right, Max Air, Sleep Right, Mute, Nozovent).

## **11. Costs**

*a. Detail costs of study procedure(s) or drug (s) or substance(s) to participants and identify who will pay for them.*

The cost of the nasal dilators for participants will be borne by the research team including the principal investigator.

